#### Two to Five years post randomisation;

**Primary Aim:** The primary outcome is criminal conviction as registered on the Police National Computer.

**Secondary Aim:** Secondary outcomes will include (a) antisocial behaviour as indicated by arrest, cautions, self-report, (b) emotional well-being, including the presence or absence of psychiatric problems, (c) education and training outcomes, (d) social network, specifically the quality of relationships with parents and peers (e) self-efficacy (f) physical health, together with (g) work adjustment and (h) early (unplanned) pregnancy or fatherhood. The use of services and associated costs will be monitored. We will estimate the total social, health, educational and criminal justice cost of interventions at 48 months post-randomisation, when we will also identify the key cost and outcome drivers and value for money of the treatments.

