Our primary outcome is incidence of out of home care, but we recognize that out of home care cannot be considered a negative outcome in all cases. We have therefore identified key forensic, family function and individual well being indicators which will be assessed at 6, 12, 18, 24, 36and 48 months after randomisation. It is important to delimit as far as possible the key moderators of the effects of MST and we will explore the moderating effects of callous and unemotional traits and severity of anti-social behaviour. In order to understand the way this new intervention impacts on current services, from the viewpoint of both the users and providers, we will also undertake a qualitative, interview based investigation of the key stakeholders in the service systematically sampled from the 9 sites.

**Design:** This will be a randomised controlled trial. Allocation will be by minimisation, controlling for number of past convictions, gender and age at onset of criminal behaviour. Minimisation will be necessary to limit the impact of factors that could easily influence treatment response. Treatment centre will also be included in the minimization stratification to control for differences between centres. Recruitment and treatment will take 18 months. Treatments will be offered over a period of three to six months for individual families. The primary outcome will be out of home placements at 18 months. Key outcomes will include court or pre-court disposal rates as at 18 months following randomisation with further follow-ups included in the initial consent, as long-term prevention is a central goal of the intervention. Other secondary endpoint measures will be total service and criminal justice sector costs over 18 months post-randomisation, wellbeing, drug misuse, and family functioning.

**Setting:** Treatments will be offered by services collaborating in this MST trial at the 9 pilot sites. The study will be conducted in three research hubs or centres: London (UCL and IoP), Cambridge and Leeds. Cambridge and Leeds will be responsible for data collection from 5 pilot sites while London will collect from 4, selected on the basis of geographical convenience.

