2) a person voices a fixed intention to harm a specific other person that must be communicated to the police; or 3)the information is demanded by the judge; and

That at six-month, one-year, two-year and three-year intervals the law-breaking behavior of the young person will be checked and that this information will not be revealed to anyone outside the research group.

The verbal explanation of the study given by the MST Supervisor, MST Therapists and Outcomes Assessor to the young person and her/his parent or carer is a crucial part of the process whereby they are able to give valid consent to take part in the study. In seeking consent, the MST Supervisor, MST Therapists and Outcomes Assessor ensure the decision is made on an informed basis. Due to the vulnerability of the young person and her/his parent or principal carer, there are a number of potential misunderstandings that could lead to their giving consent on an uninformed basis and to which the MST Supervisor, MST Therapists and Outcomes Assessor must be alert, namely:

1. The young person and her/his parent or carer may think they are obliged to take part because the study is part of the young person's sentence, i.e. they may not understand the voluntary nature of the study.

2. They may think that refusal to participate will have further negative consequences for the young person.

3. They may think that if they drop out of the study that this will have negative consequences for the young person, for instance that the young person will be breached and taken back to court.

4. They may think that agreement to participate means that they automatically get MST.

5. They may not understand that the MST intervention involves the participation of the parent or carer as well as the young person.

6. The young person and his/her parent or carer may not realise the young person's decision as to whether to participate carries the same weight as the parent or principal carer and that, if the young person refuses to give consent, participation cannot go ahead even if the parent or carer agree to give their consent.

7. The capacity of the young person to understand the nature of the study will vary accoriding to her/his age. For example, a young person aged 13 years is unlikely to understand or grasp the nature of the study in the same way as a young person aged 16 years.

To guard against these and other pitfalls MST Supervisor, MST Therapists and Outcomes Assessor considers the following action points:

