#### **Measures:**

Follow-up assessments will be at 6, 12, 18, 24, 36 and 48 months post randomisation, with primary outcomes collected until 5 years post randomisation.

(a) Principles of measurement: The measures will be made across multiple domains (specific to criminal behaviour, family function, user satisfaction, comorbid problems and economic costs), using multiple methods (interviews, questionnaires, records), and multiple sources (adolescent, parent, teachers) to maximise the clinical validity of the outcome assessments and minimise bias arising from any single source of information. Where possible, measures will be made by individuals blind to treatment allocation. Many of the measures have been selected because they are part of an ambitious project under-way in the Parenting Academy (Scott, Dabbs et al.) with a range of samples, including with a large sample of looked after children, which will provide UK norms against which the current sample may be compared.

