
There may be further concerns attached to using out of home placement as a primary outcome. It is possible to envision a situation whereby the presence of the MST team would influence the likelihood of court or other systems deciding to place the young person away from the family. It is also possible that the presence of the MST team, affording a more accurate view of family function, may precipitate the placement of the young person outside the home. These types of influences which suggest that the primary outcome measure may be 'reactive' with the planned intervention would compromise randomisation, and compromise the trial. In order to minimise these problems we have placed the endpoint of the study at 18 months in order to see if the impact of MST may be felt over the course of the year that follows the intervention. It is unlikely that over this period the measure (long-term placement out of home) would be reactive with the intervention.

The other domains we consider key to the intervention are (a) forensic outcomes, (b) adolescent wellbeing outcomes and (c) family functioning outcomes. In addition of course, in line with the research brief, we consider the economic data collected alongside these outcomes to be key.

*Key Forensic Outcome:* We have considered a range of forensic outcomes related to the antisocial behaviors which remain a key part of the definition of the target population. Perhaps the most meaningful key forensic outcome would be reconviction rates which over a short term follow-up based on 3 studies favours MST compared to standard care with an RR of .51, (95%CI .23, 1.16). The likelihood of reconviction during the course of treatment is 30% and over 18 months from randomisation is about 50% based on a combination of US and Canadian studies. We will use time to offences (categorised as per annual statistical reports Youth Justice Board, 2007) that resulted in a pre-court disposal (Reprimand or Final Warning) or a court disposal. Access to this information will have been approved by the YJB. In collaboration with the YJB, we will also examine whether MST reduces use of custodial sentences and hence service costs.

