#### Design and Methodology (Annual follow up from 2-5 years)

The annual follow-up period from 2 years post randomisation will extend the primary outcome window to 60 months and carry out an evaluation of a broadened range of outcomes of both MST and MAU to 48 months. We will conduct annual full-blind outcome evaluations up to 48 months post-randomisation. Data on service use will be collected using the Child and Adolescent Service Use Schedule (CA-SUS) and Children & Young People, Resources, Evaluation and Systems Schedule (CYPRESS) (Pilling et al., 2012). Data will be used to characterise services and provide currently lacking information on transitions from child to adult services, identifying correlates of a smooth transition (continuation of appropriate services across the 18-year barrier) and testing the hypothesis that transition is important to relatively better outcomes. A a semi-structured interview will explore young people's and primary caregivers' views of change or the absence of change in key outcome domains and the families experiences of services and of the transition between services.

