## Data analysis (annual follow up 2-5 years)

The primary outcome, time to first conviction, will be described by a Kaplan-Meier graph and summarised by the proportion with convictions by 60 months. Cox regression adjusting for pre-specified key predictors will estimate treatment effects. Secondary outcomes up to 48 months post-randomisation will be analysed by linear or logistic regression as appropriate. We will also use random effects models to explore differences between randomised groups in trajectories over time. Data on service use collected using the CA-SUS will be supplemented by a critical pathway analytic approach mapping participants' journey from initial referral to experience of adult services

The primary economic evaluation will explore cost-effectiveness in terms of the primary outcome. A cost-utility analysis will also be undertaken, using QALYs calculated using the EQ-5D (EuroQol) measure of health related quality of life (Brooks.,1996)). Analyses will be undertaken from a societal perspective. Cost-effectiveness will be explored initially by calculating incremental cost effectiveness ratios (ICERs) –difference in mean costs divided by difference in mean effects (Van Hout.,1994). Repeat re-sampling from the costs and effectiveness data will then be used to generate a distribution of mean costs and effects for the two treatments, which can be used to calculate the probability that each of the treatments is the optimal choice, subject to a range of possible maximum values (ceiling ratio) that a decision-maker might be willing to pay for a unit improvement in outcome. Cost-effectiveness acceptability curves will be presented by plotting these probabilities for a range of possible values of the ceiling ratio Fenwick et al., 2001).

The qualitative interviews will all be transcribed before undergoing a synthesis of IPA and framework analysis ([name]., 2009; Ritchie., 1994) as successfully employed in [name]'s previous

funded health research. This enables analysis to begin with a closely focused and psychological examination of the first set of transcripts using IPA. This then feeds into a framework analysis of subsequent transcripts as the balance shifts from an inductive to a more deductive phase and accommodates a large amount of qualitative data. This hermeneutic circle of analysis is completed by a final micro analysis of selected subset of cases illuminated by the complete corpus analysis.

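### The consent explanation describes criminal-record checks up to three years, but the primary outcome of the 2-5 year phase is conviction up to 60 months

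*Protocol*

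**What the plan says.** The protocol gives two horizons for looking at criminal records.

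- **What families are told.** Methods of recruitment and consent sets out the points that a potential participant has to understand. On records, the point is that "at six-month, one-year, two-year and three-year intervals the law-breaking behavior of the young person will be checked". The same section treats the spoken explanation as central to valid consent, warns against consent given without proper information, and notes that understanding varies with the young person's age.
- **What the long-term phase needs.** Under Two to Five years post randomisation: "The primary outcome is criminal conviction as registered on the Police National Computer". The Measures section describes follow-up "with primary outcomes collected until 5 years post randomisation". The design section for the annual follow-up says that this phase "will extend the primary outcome window to 60 months". The matching data analysis section has time to first conviction "summarised by the proportion with convictions by 60 months".

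Two other statements bear on the scope of consent. The Design paragraph refers to "court or pre-court disposal rates as at 18 months following randomisation with further follow-ups included in the initial consent". The paragraph on risks and benefits says that families will agree to give access to arrest and conviction records. Neither says for how long.

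**The concern.** Staff who follow the consent section as written give young people and carers a three-year horizon for record checks, while the primary outcome of the later phase is read from those records up to five years. Both statements stand in the current text.

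What is at stake is complete ascertainment. Under Participant Adherence, the protocol relies on formally recorded primary outcomes because they can be obtained even for people who have left treatment and research appointments. The same advantage makes a register-based conviction outcome attractive over five years. If it emerged that access after month 36 needed fresh agreement, the outcome for that period would depend on re-contact. Young people who are in custody or hard to trace would plausibly be the ones missing, and they are unlikely to resemble the rest in conviction risk.

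The matter also concerns the records of minors. Entry is at 11 to 17 years, so participants are 11 + 5 = 16 to 17 + 5 = 22 years old at 60 months. Many will have become adults by then.

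**Working it through.** No sample size, power or error-rate figure is involved, so there is no figure in the plan to reproduce. The check sets the two schedules side by side.

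**Inputs, all from the protocol**

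- Record checks described to families (Methods of recruitment and consent): 6, 12, 24 and 36 months.
- Key forensic outcome of the first phase (Design paragraph): 18 months, analysed as a time to event ("We will use time to offences").
- Primary outcome of the 2-5 year phase (Measures; Annual follow up from 2-5 years; Data analysis for that period): 60 months.

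**Step 1: the 60-month outcome.** Last check described = 36 months. End of the outcome window = 60 months. Gap = 60 - 36 = 24 months. Share of the window = 24 / 60 = 40%.

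**Step 2: the 18-month outcome.** Month 18 is not in the list, but 12 < 18 < 24, and 24 lies inside the three-year span. Provided the records carry offence or disposal dates (an assumption, though a time-to-offence analysis needs them), the check described at 24 months reaches back over the whole 18-month window. The missing time point is a matter of wording and leaves no gap in the period described.

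**Step 3: whether other text supplies the missing horizon.**

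| Place in the protocol | What it offers | End date given? |
|---|---|---|
| Design paragraph | Further follow-ups within the initial consent | None |
| Risks and anticipated benefits | Agreement to access to arrest and conviction records | None |
| Sections on the 2-5 year phase | Outcomes, measures and analysis; no re-consent step | Not applicable |

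The only horizon that the protocol tells staff to give families for record checks is therefore three years.

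**The case against.** The strongest reply is that the consent section lists times at which checks will happen and does not exclude others. The Design paragraph and the paragraph on risks both point to broader consent. The operative documents are the information sheets and consent forms, which staff go through with the family and which are not part of the text reviewed. On this view the list is recruitment wording that was not updated when the long-term phase was written in, and the signed forms may already reach five years.

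Most of that stands, and it limits the point. A reader might infer any of the following, and the documents support none of them:

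- **That families are promised no checks after three years.** The text contains no such limit.
- **That the consent obtained does not cover the 60-month outcome.** This cannot be decided without the forms, and their absence from the reviewed text is no defect of the plan.
- **That the 18-month forensic outcome is also uncovered.** It falls inside the three-year span, and dated records would capture it.
- **That a given share of first convictions is at risk.** Such a figure would have to start from the reconviction rate of about 50% over 18 months in the forensic outcome section. That rate comes from US and Canadian studies, whereas this trial also admits young people with no conviction. It would also need an assumed constant hazard, and those events would be at risk only if consent did fall short.

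The young person's right to refuse record access at any time is a separate safeguard that would apply under any schedule, so it does not add to the conflict.

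The reply does not remove the mismatch itself. The section that defines what participants have to understand stops two years short of a primary endpoint, and neither of the broader statements gives the missing horizon.

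**Conclusion.** The point holds as an internal inconsistency with a practical consequence. The record-check schedule that staff must explain ends at 36 months, the primary outcome of the later phase runs to 60 months, and 24 of the 60 months (40%) lie beyond the last check described. That figure follows directly from the protocol's own times and needs no further assumption.

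The effect on the data is conditional. Complete register ascertainment after month 36 is at risk only if the signed consent does not reach that far, which the text does not settle. The expectation that those missing would differ in conviction risk is a judgement; the protocol gives no figure for it. No estimand, analysis model or sample size is misstated. The mismatch still deserves correction because it concerns a primary outcome drawn from young people's criminal records, and because any agreement still needed is easier to obtain before month 36 than afterwards.

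**What to change.** 1. In Methods of recruitment and consent, replace the listed check times with the record-check window that the trial uses, from randomisation to 60 months, so that the explanation agrees with the Measures section and both sections on the 2-5 year phase.
2. State in the protocol which consent covers record access from 36 to 60 months, and give the horizon where the Design paragraph mentions follow-ups within the initial consent.
3. Check the signed forms against that window. If they already cover 60 months, the text correction is enough. If they do not, obtain documented agreement at the existing 24- or 36-month assessment.

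The cost is a wording change with its ethics amendment and, only if the forms fall short, one added form at a visit already planned. The small downside of asking again is that a few participants may decline.

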
Whilst the 2007 review by Utting et al. (Utting et al., 2007) was also positive in identifying MST as an evidence-based approach for children at risk of developing antisocial personality disorder and associated problems including substance misuse and time spent in custody, a number of issues emerge from reviews of these studies that point to issues for further exploration in an RCT: (1) inflation of effect sizes in some trials because of exclusion of participants who did not engage with MST (i.e. a failure to do intent-to-treat analyses); (2) the possible influence in efficacy trials of the developer's deep involvement and commitment to the success of the intervention, and the feasibility of transporting treatments that require such intensive supervisory oversight from the developers to real-world settings; (3) the importance of developer involvement in ensuring adherence to the nine MST treatment principles that are believed to account for the effect size difference between efficacy (d=.81) and effectiveness studies (d=.26); (4) the extent to which the 9 MST principles discriminate MST from standard care, particularly as many standard care packages in the UK share these principles which are principles of good practice not unique to MST (a schematic current care pathway for young people in the UK is given in figure 1 below); (5) the absence of empirical data to demonstrate that the MST therapist adherence measure (TAM)

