1. Those who have agreed to discuss the study having received the MST information leaflets may sign the consent form at the first meeting with the MST Supervisor, MST Therapists and Outcomes Assessor. Some potential participants may express an interest in the study but prefer to have time to think over their participation.

2. At the meetings, the pitfalls described above should be addressed as part of the explanation of the study given to the young person and her/his parent or carer.

3. Before the consent forms are signed, the MST Supervisor goes through the information sheet and the consent forms with the parent or carer to ensure she/he understands the study. The MST Therapist, who like the MST Supervisor is trained to work with young people, goes through the information sheet with the young person. the MST therapist interprets the information sheet to ensure that the young person understands what is involved: that her/his participation is entirely voluntary; that she/he can withdraw from the study at any time without being penalised; that at any time she/he can refuse to have her/his criminal record accessed; that should she/he get MST, this intervention is independent of services offered by the YOS; that we may offer to help in a number of areas, including education, social activities, substance abuse and anger management if these are problems that contribute to her/him getting into trouble but that he/she can refuse help in one area without jeopardising help in other areas.

Finally, the MST supervisor and therapists follow the following guidelines regarding withdrawal from the study by the young person and her/his parent or carer:

1. The decision of the young person and her/his parent or carer to withdraw from the clinical trial should at all times be respected.

2. If the young person and her/his parent or carer consistently refuse to carry out recommendations of the MST therapist, this should be interpreted as them not wanting to continue with the project.

 If the young person and her/his parent or carer consistently refuse to make appointments with the MST Therapist, this should be interpreted as not wanting to continue with the project.
 Withdrawal from the study is a barrier to future participation.

5. The data from the participants who withdraw consent should be kept until the end of the study. Once the study is over their data must be removed.

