Planned Intervention: Multi-systemic therapy is an integrative, manualised, licensed programme with a substantial evidence base for engaging young people exhibiting anti-social behaviour and their families. Adolescents with severe conduct problems (violence, drug abuse, school expulsion) will be treated over a period of 3-6 months with a community-based multicomponent treatment programme focused on the family but also engaging schools, neighbourhoods and community resources and administered by specifically trained professionals with relatively low caseloads. Young people and families requiring this approach are assumed to be resistant to engagement by existing services even though intensive outreach services may be required, probably associated with complex family problems including substance misuse and mental health problems that are likely to affect parenting. Adolescents and their families will receive a minimum of 3 and a maximum of 6 months of input from the MST team. The frequency of contact with the MST workers will be monitored but not controlled. It is expected that, as with MAU, some families will require briefer periods of treatment or may prematurely terminate treatment unilaterally. MST is going to be delivered by a team of at least 3 specially trained clinicians under the supervision of an MST supervisor, with weekly one hour conference calls for consultation with an MST services staff member. In addition, it is expected that MST therapists will have the support of local consultation from mental health professionals with post-graduate qualifications in disciplines such as social work, psychology or counselling. In view of the breadth and complexity of this input, it will be essential to monitor consultation as well as contact time of the MST team in order to arrive at accurate assessments of health and social care costs. It is essential that MST therapists and MST supervisors should not be allowed to see participants in the MAU arm of the trial, although professional consultants to the MST team may well be engaged in provision of MAU.

*Management as usual* MAU will be the standard care offered to adolescents and their families who meet eligibility criteria for the trial. This treatment is likely to be diverse and may involve no therapeutic intervention or individual or family orientated work. It is likely to be delivered by a wide range of practitioners with quite different theoretical orientations. The average duration of

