#### Participant Adherence:

Dropping out of treatment is common during interventions for antisocial problems (Kazdin & Wassell, 2000; Kazdin & Wasser, 2000) MST has a far superior record of maintaining cases in treatment when compared with MAU (86% vs 79%). Based on 6 studies the RR is highly significantly favouring MST (RR=.69, 95% CI: 0.49, .98). In the BCT following the careful recruitment procedure outlined above, well over 90% of those recruited for either arm of the trial have been retained for the purposes of data collection. We recognise that participation in the various treatment protocols will have lower adherence than data collection as data collection visits are incentivised for both families and young persons by modest compensation for time and travel. To ensure a comprehensive intent to treat analysis the primary outcomes consist of data recorded formally (e.g. out of home placements) which can be measured even if participants have dropped out of treatment and research appointments. In the current trial we have conservatively assumed a 5% dropout at each measurement point, totalling a 15% attrition overall that would effect analysis of secondary outcomes (see Figure 2).

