**Data analysis (randomisation to 18 month follow up):** The primary outcome, out-of-home placement, will be described by a Kaplan-Meier graph and summarised by the proportions with out-of-home placement by 18 months. The primary analysis will be Cox regression, adjusting for key predictors which will be pre-specified from a list including centre, site, the minimisation variables, and other risk indicators. We will use interaction tests to explore whether the intervention effect differs according to pre-specified sub-grouping variables (gender, age, presence of criminal record and referral path). Clustering by therapist will be allowed for by computing robust standard errors (but these will be ignored if they turn out to be smaller than conventional standard errors) (Roberts, 1999). Secondary outcomes at each time will be analysed by linear or logistic regression as appropriate. We will also use random effects models to explore differences between randomised groups in trajectories over time. Analyses will be by intention-to-treat: that is, including each individual in their randomised group regardless of the intervention actually received, and performing sensitivity analyses to explore the impact of any missing data.

*Health economics data analysis:* Despite the often skewed nature of costs, mean costs will be compared using standard parametric tests and the robustness of the results confirmed using bootstrapping (Efron & Tibshirani, 1993). The advantage of this approach, as opposed to logarithmic transformation or non-parametric tests, is the ability to make inferences about the arithmetic mean, which is more meaningful from a budgetary perspective (Thompson & Barber, 2000). Details of special school placement will also be recorded as part of the economic data collection. Because schools vary greatly, we generally ask for specific details regarding all non-mainstream schools, including name and address of school so that we can check/verify the type of school, as necessary.

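### The withdrawal guidelines let non-engagement with MST count as leaving the study, which can end follow-up for non-engagers in the MST arm only and contradicts intention-to-treat

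*Protocol*

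**What the plan says.** The Protocol's section on methods of recruitment and consent ends with a numbered list, introduced by saying that "the MST supervisor and therapists follow the following guidelines regarding withdrawal from the study". Item 2 covers families who "consistently refuse to carry out recommendations of the MST therapist, this should be interpreted as them not wanting to continue with the project". Item 3 covers those who "consistently refuse to make appointments with the MST Therapist, this should be interpreted as not wanting to continue with the project". Item 4 makes study withdrawal a bar to taking part later. Item 5 concerns participants who withdraw consent: their data are held until the study ends, and then "Once the study is over their data must be removed".

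Other sections say the following.

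- **Data analysis (randomisation to 18 month follow up):** intention-to-treat, "including each individual in their randomised group regardless of the intervention actually received".
- **Participant Adherence:** the primary outcome rests on formally recorded data "which can be measured even if participants have dropped out of treatment and research appointments".
- **Methods of recruitment and consent, earlier:** carers and young people must be told that they may leave the MST condition.
- **Planned Intervention:** as with MAU, it is expected that "some families will require briefer periods of treatment or may prematurely terminate treatment unilaterally". MST therapists and supervisors must not see MAU participants.
- **Systematic Review of MST:** some earlier trials are said to have inflated effects because of "exclusion of participants who did not engage with MST (i.e. a failure to do intent-to-treat analyses".

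**The concern.** Stopping a treatment and leaving a trial are different events, and intention-to-treat depends on keeping them apart. Items 2 and 3 merge them. Staff who deliver the tested treatment, and who know the allocation, infer a wish to leave the project from a family's behaviour towards that treatment.

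The trigger is behaviour towards an MST therapist, so no MAU family can meet it, and no equivalent rule is written for MAU. If the guidelines are followed literally, follow-up can be lost in one arm for a reason tied to engagement. That is the exclusion for which the Protocol criticises earlier MST trials. The planned sensitivity analyses for missing data can explore such a loss, but they cannot restore observations that were never collected.

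**Working it through.** **1. The plan's own figure.** The Procedure and Sample size section gives 350 per arm, 30% versus 20%, and power of 86%, or 83% after design effects of 1.22 (MST) and 1 (MAU). Two-sided alpha of 0.05 is assumed, since it is not stated.

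- Standard error under the null: √(0.25 × 0.75 × 2/350) = 0.0327.
- Standard error under the alternative: √((0.30 × 0.70 + 0.20 × 0.80)/350) = 0.0325.
- z = (0.10 − 1.96 × 0.0327)/0.0325 = 1.10, so power is 86.5%.
- With the MST arm deflated to 350/1.22 = 287, power is 82.6%.

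Both figures reproduce, so the sample size is not at fault. They presuppose that all 350 per arm contribute.

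**2. Can only one arm meet the trigger?** Items 2 and 3 require refusal of an MST therapist. MST therapists may not see MAU participants. The rule therefore acts in the MST arm only. Ordinary withdrawal and attrition can still occur in both arms.

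**3. Illustration of size.** Let d be the share of the MST arm dropped from the analysis and r their placement risk. With no true effect and 30% risk in both arms:

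observed MST rate = (0.30 − d × r)/(1 − d)

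The values of d are assumptions. The 14% is 100% − 86%, from the MST treatment retention in earlier studies quoted under Participant Adherence. The 5% is a lower value, in keeping with that section's statement that well over 90% in either arm of the Brandon Centre trial were retained for data collection. The values of r have no source in the Protocol and are shown as a range.

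| d | r | Observed MST rate | Spurious benefit (points) | Two-sided rejection |
|---|---|---|---|---|
| 5% | 30% | 30.0% | 0 | 5.0% |
| 5% | 40% | 29.5% | 0.5 | 5.3% |
| 5% | 50% | 28.9% | 1.1 | 6.0% |
| 5% | 60% | 28.4% | 1.6 | 7.4% |
| 14% | 30% | 30.0% | 0 | 5.0% |
| 14% | 40% | 28.4% | 1.6 | 7.4% |
| 14% | 50% | 26.7% | 3.3 | 15.0% |
| 14% | 60% | 25.1% | 4.9 | 28.3% |

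For the last row: (0.30 − 0.14 × 0.60)/0.86 = 0.216/0.86 = 0.251. Rejection rates use a pooled two-proportion test with 350 MAU and 350 × (1 − d) MST participants. They ignore therapist clustering and are not the planned Cox model.

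**4. The other direction.** With d = 14% and r = 20%, the observed MST rate is 0.272/0.86 = 31.6%. With r = 10% it is 0.286/0.86 = 33.3%. The bias then runs against MST by 1.6 and 3.3 points.

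**The case against.** The strongest reply is that the wording is loose but the trial's data are protected. Several parts of it stand.

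- A reader might infer that non-engagers' data are deleted. The text does not say so. Item 5 covers participants who withdraw consent, while items 2 and 3 never call refusal a withdrawal of consent. Item 5 also holds the data until the study ends, which permits their use in the trial analysis.
- A reader might infer that the primary comparison is broken. Participant Adherence says the primary outcome survives drop-out from treatment and from research visits, and the Measures section describes placement as collectable on the whole sample. If that is what happens, the harm falls mainly on interview-based secondary outcomes.
- A reader might take bias towards MST as certain. The Protocol's own criticism of earlier trials makes that direction plausible, but it requires non-engagers to be at above-average risk. At average risk the bias is zero, and below it the sign reverses.
- A reader might see a clash between item 5 and the 20-year retention of trial documentation. Archiving trial records does not rule out removing the data of people who withdrew consent, so this is not pressed.
- The 14% is treatment non-retention in other studies, not the share who would consistently refuse MST and then be dropped.
- The list addresses MST supervisors and therapists, and does not name the outcome assessors who collect follow-up data.

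The reply does not remove the contradiction. The list is expressly about study withdrawal, it refers to the project and not to the therapy, and nothing in it tells site staff that follow-up continues.

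**Conclusion.** The concern holds as a contradiction in the conduct rules. Items 2 and 3 of the withdrawal guidelines can end follow-up for MST non-engagers only, against the intention-to-treat statement, the stated follow-up of treatment drop-outs and the separate freedom to leave the MST condition.

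Interview-based secondary outcomes are most exposed. Whether the primary outcome is affected depends on whether placement records continue to be collected and kept for these families, which the Protocol does not settle.

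The size cannot be derived from the Protocol. If these families were left out of the analysis, with 30% risk and no true effect, the spurious benefit would be 0 to 1.6 points at 5% loss and 0 to 4.9 points at 14% loss, for non-engager risks of 30% to 60%. The upper end is about half the 10-point design difference. If the families stay in follow-up, this rule adds no bias and the stated power is unaffected by it.

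**What to change.** Reword items 2 and 3 so that:

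- non-engagement with MST is recorded as treatment non-adherence;
- the participant stays in all follow-up assessments and record-based outcomes and is analysed as randomised;
- only an explicit request by the young person or carer counts as study withdrawal, recorded separately for visits and for access to records;
- the same rule applies in both arms.

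In item 5, state that removal does not apply to families merely deemed not to be engaging. State also that data collected before an explicit withdrawal enter the trial analysis as far as the consent given allows. None of this touches when MST itself should end.

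The cost is a change of protocol wording and a short instruction to sites. An ethics amendment may be needed if the consent wording is affected, which cannot be judged from the Protocol alone. The planned sample size and visit schedule do not change.
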